**Urine**

22. **Normal urine:**

- Negative urine glucose, and
- Negative or trace urine protein, and
- Negative or trace urine hemoglobin (if trace hemoglobin is present on dipstick, a microscopic urinalysis with red blood cells levels within institutional normal range).

**Reproductive Status**

23. **Volunteers who were born female:** negative serum or urine beta human chorionic gonadotropin ( $\beta$ -HCG) pregnancy test performed prior to vaccination on the day of initial vaccination. Persons who are NOT of reproductive potential due to having undergone total hysterectomy or bilateral oophorectomy (verified by medical records), are not required to undergo pregnancy testing.

24. **Reproductive status:** A volunteer who was born female must:

- Agree to consistently use effective contraception (Appendix A) for sexual activity that could lead to pregnancy from at least 21 days prior to enrollment through the last required protocol clinic visit. Effective contraception is defined as using the following methods:
  - Condoms (male or female) with or without a spermicide,
  - Diaphragm or cervical cap with spermicide,
  - Intrauterine device (IUD),
  - Hormonal contraception, or
  - Any other contraceptive method approved by the HVTN 114 PSRT
  - Successful vasectomy in the male partner (considered successful if a volunteer reports that a male partner has [1] documentation of azoospermia by microscopy, or [2] a vasectomy more than 2 years ago with no resultant pregnancy despite sexual activity postvasectomy);
- Or not be of reproductive potential, such as having reached menopause (no menses for 1 year) or having undergone hysterectomy, bilateral oophorectomy, or tubal ligation;
- Or be sexually abstinent.

25. **Volunteers who were born female must also agree not to seek pregnancy through alternative methods**, such as artificial insemination or *in vitro* fertilization until after the last required protocol clinic visit

## 7.2 Exclusion criteria

### General

1. **Blood products** received within 120 days before first vaccination
2. **Investigational research agents** received within 30 days before first vaccination
3. **Body mass index (BMI)  $\geq 40$**
4. **Volunteer has 2 or more of the following cardiac risk factors:**
  - Participant report of history of elevated blood cholesterol defined as fasting LDL  $>160$  mg/dL;
  - First degree relative (eg, mother, father, brother, or sister) who had coronary artery disease before the age of 50 years;
  - Current smoker; or
  - BMI  $\geq 35$
5. **Pregnant or breastfeeding**
6. **Active duty and reserve US military personnel**

### Vaccines and other Injections

7. **Any clinically significant AE related to vaccination in HVTN 205**, for which revaccination would be a safety concern such as any grade 3 or 4 related AE
8. **Smallpox vaccine** received within the last 5 years
9. **HIV vaccine(s)** received in a prior HIV vaccine trial other than HVTN 205. For HVTN 205 participants who have subsequently received control/placebo in another HIV vaccine trial, the HVTN 114 PSRT will determine eligibility on a case-by-case basis.
10. **Non-HIV experimental vaccine(s) received within the last 5 years** in a prior vaccine trial. Exceptions may be made for vaccines that have subsequently undergone licensure by the FDA. For volunteers who have received control/placebo in an experimental vaccine trial, the HVTN 114 PSRT will determine eligibility on a case-by-case basis. For volunteers who have received an experimental vaccine(s) greater than 5 years ago, eligibility for enrollment will be determined by the HVTN 114 PSRT on a case-by-case basis.

11. **Live attenuated vaccines** other than influenza vaccine received within 30 days before first vaccination or scheduled within 14 days after injection (eg, measles, mumps, and rubella [MMR]; oral polio vaccine [OPV]; varicella; yellow fever)
12. **Influenza vaccine or any vaccines that are not live attenuated vaccines** and were received within 14 days prior to first vaccination (eg, tetanus, pneumococcal, Hepatitis A or B)
13. **Allergy treatment with antigen injections** within 30 days before first vaccination or that are scheduled within 14 days after first vaccination

### **Immune System**

14. **Immunosuppressive medications** received within 168 days before first vaccination. (Not exclusionary: [1] corticosteroid nasal spray; [2] inhaled corticosteroids; [3] topical corticosteroids for mild, uncomplicated dermatitis; or [4] a single course of oral/parenteral corticosteroids at doses < 2 mg/kg/day and length of therapy < 11 days with completion at least 30 days prior to enrollment.)
15. **Serious adverse reactions to vaccines or to vaccine components**, including history of anaphylaxis and related symptoms such as hives, respiratory difficulty, angioedema, and/or abdominal pain. (Not excluded from participation: a volunteer who had a nonanaphylactic adverse reaction to pertussis vaccine as a child.)
16. **Hypersensitivity to eggs or egg products**
17. **Immunoglobulin** received within 60 days before first vaccination
18. **Autoimmune disease** (eg, myositis)
19. **Immunodeficiency**

### **Cardiac**

20. **History of myocarditis, pericarditis, cardiomyopathy, congestive heart failure with permanent sequelae, clinically significant arrhythmia** (including any arrhythmia requiring medication, treatment, or clinical follow-up)
21. **ECG with clinically significant findings**, or features that would interfere with the assessment of myo/pericarditis, as determined by a contract ECG Lab or cardiologist, including any of the following: (1) conduction disturbance (complete left or complete right bundle branch block or nonspecific intraventricular conduction disturbance with QRS  $\geq$  120 ms, PR interval  $\geq$  220ms, any 2nd or 3rd degree AV block, or QTc prolongation (> 450ms)); (2) repolarization (ST segment or T wave) abnormality that will interfere with the assessment of myo/pericarditis; (3) significant atrial or ventricular arrhythmia; (4) frequent atrial or ventricular ectopy (eg, frequent premature atrial contractions, 2 premature ventricular contractions in a row); (5) ST elevation consistent with ischemia; (6) evidence of past or evolving myocardial infarction

### **Clinically significant medical conditions**

22. **Untreated or incompletely treated syphilis infection**

23. **Clinically significant medical condition**, physical examination findings, clinically significant abnormal laboratory results, or past medical history with clinically significant implications for current health. A clinically significant condition or process includes but is not limited to:
- A process that would affect the immune response,
  - A process that would require medication that affects the immune response,
  - Any contraindication to repeated injections or blood draws,
  - A condition that requires active medical intervention or monitoring to avert grave danger to the volunteer's health or well-being during the study period,
  - A condition or process for which signs or symptoms could be confused with reactions to vaccine, or
  - Any condition specifically listed among the exclusion criteria below.
24. **Any medical, psychiatric, occupational, or other condition** that, in the judgment of the investigator, would interfere with, or serve as a contraindication to, protocol adherence, assessment of safety or reactogenicity, or a volunteer's ability to give informed consent
25. **Psychiatric condition that precludes compliance with the protocol.** Specifically excluded are persons with psychoses within the past 3 years, ongoing risk for suicide, or history of suicide attempt or gesture within the past 3 years.
26. **Current anti-tuberculosis (TB) prophylaxis or therapy**
27. **Asthma** other than mild, well-controlled asthma. (Symptoms of asthma severity as defined in the most recent National Asthma Education and Prevention Program (NAEPP) Expert Panel report).
- Exclude a volunteer who:
- Uses a short-acting rescue inhaler (typically a beta 2 agonist) daily, or
  - Uses moderate/high dose inhaled corticosteroids, or
  - In the past year has either of the following:
    - Greater than 1 exacerbation of symptoms treated with oral/parenteral corticosteroids;
    - Needed emergency care, urgent care, hospitalization, or intubation for asthma.
28. **Diabetes mellitus** type 1 or type 2, including cases controlled with diet alone. (Not excluded: history of isolated gestational diabetes.)
29. **Thyroidectomy, or thyroid disease** requiring medication during the last 12 months
30. **Hypertension:**

- If a person has been found to have elevated blood pressure or hypertension during screening or previously, exclude for blood pressure that is not well controlled. Well-controlled blood pressure is defined as consistently  $\leq 140$  mm Hg systolic and  $\leq 90$  mm Hg diastolic, with or without medication, with only isolated, brief instances of higher readings, which must be  $\leq 150$  mm Hg systolic and  $\leq 100$  mm Hg diastolic. For these volunteers, blood pressure must be  $\leq 140$  mm Hg systolic and  $\leq 90$  mm Hg diastolic at enrollment.
  - If a person has NOT been found to have elevated blood pressure or hypertension during screening or previously, exclude for systolic blood pressure  $\geq 150$  mm Hg at enrollment or diastolic blood pressure  $\geq 100$  mm Hg at enrollment.
31. **Bleeding disorder** diagnosed by a doctor (eg, factor deficiency, coagulopathy, or platelet disorder requiring special precautions)
  32. **Malignancy** (Not excluded from participation: Volunteer who has had malignancy excised surgically and who, in the investigator's estimation, has a reasonable assurance of sustained cure. or who is unlikely to experience recurrence of malignancy during the period of the study)
  33. **Seizure disorder:** History of seizure(s) within past three years. Also exclude if volunteer has used medications in order to prevent or treat seizure(s) at any time within the past 3 years.
  34. **Asplenia:** any condition resulting in the absence of a functional spleen
  35. History of hereditary **angioedema**, acquired angioedema, or idiopathic angioedema.

### 7.3 Participant departure from vaccination schedule or withdrawal

This section concerns an individual participant's departure from the vaccination schedule. Pause rules for the trial as a whole are described in Section 11.3.

#### 7.3.1 Delaying vaccinations for a participant

Under certain circumstances, a participant's scheduled vaccination will be delayed. The factors to be considered in such a decision include but are not limited to the following:

- Within 45 days prior to any study injection
  - Receipt of blood products or immunoglobulin
- Within 30 days prior to any study injection
  - Receipt of live attenuated vaccines other than influenza vaccine
  - Receipt of allergy treatment with antigen injections
- Within 14 days prior to any study injection
  - Receipt of influenza vaccine or any vaccines that are not live attenuated vaccines (eg, pneumococcal)

- Pre-vaccination abnormal vital signs or clinical symptoms that may mask assessment of vaccine reaction.

Vaccinations should not be administered outside the visit window period specified in the HVTN 114 Study Specific Procedures.

In order to avoid vaccination delays and missed vaccinations, participants who plan to receive licensed vaccines or allergy treatments should be counseled to schedule receipt of these substances, when possible, outside the intervals indicated above. The effects of these substances on safety and immunogenicity assessments and their interactions with study vaccines are unknown. Therefore, if circumstances allow, these substances should also be avoided in the 2 week interval between a study vaccination and completion of the 2 weeks postvaccination follow-up visit.

### **7.3.2 Participant departure from vaccination schedule**

Every effort should be made to follow the vaccination schedule per the protocol. If a participant misses a vaccination and the visit window period for the vaccination has passed, that vaccination cannot be given. The participant should be asked to continue study visits.

### **7.3.3 Discontinuing vaccination for a participant**

Under certain circumstances, an individual participant's vaccinations will be permanently discontinued. Specific events that will result in stopping a participant's vaccination schedule include:

- Co-enrollment in a study with an investigational research agent (rare exceptions allowing for the continuation of vaccinations may be granted with the unanimous consent of the HVTN 114 PSRT).
- Clinically significant condition (ie, a condition that affects the immune system or for which continued vaccinations and/or blood draws may pose additional risk), including but not limited to the following:
  - Pregnancy (regardless of outcome);
  - Any grade 4 local or systemic reactogenicity symptom, lab abnormality, or AE that is subsequently considered to be related to vaccination;
  - Any grade 3 lab abnormality or other clinical AE (exception: fever or vomiting and subjective local and systemic symptoms) that is subsequently considered to be related to vaccination; or
  - Clinically significant type 1 hypersensitivity reaction associated with study vaccination. Consultation with the HVTN 114 PSRT is required prior to subsequent vaccinations following any type 1 hypersensitivity reaction associated with study vaccination; or
- Investigator determination in consultation with Protocol Team leadership (eg, for repeated nonadherence to study staff instructions).

Such participants should be counseled on the importance of continuing with the study and strongly encouraged to participate in follow-up visits and protocol-related procedures per the protocol for the remainder of the trial, unless medically contraindicated.

In addition, vaccinations will be stopped for participants diagnosed with HIV infection. HIV-infected participants will not continue in the trial (Sections 7.3.4 and 9.7.1).

#### **7.3.4 Participant termination from the study**

Under certain circumstances, an individual participant may be terminated from participation in this study. Specific events that will result in early termination include:

- Participant refuses further participation,
- Participant relocates and remote follow-up or transfer to another HVTN CRS is not possible,
- HVTN CRS determines that the participant is lost to follow-up,
- Participant becomes HIV infected, or
- Investigator decides, in consultation with Protocol Team leadership, to terminate participation (eg, if participant exhibits inappropriate behavior toward clinic staff).
- Any condition where termination from the study is required by applicable regulations.

## 8 Study product preparation and administration

CRS pharmacists should consult the Pharmacy Guidelines and Instructions for DAIDS Clinical Trials Networks for standard pharmacy operations. The protocol schema is shown in Table 3-1. See the Investigator's Brochures for further information about study products.

### 8.1 Vaccine regimen

The schedule of vaccination is shown in Section 3 and additional information is given below.

#### Group 1

##### Treatment 1 (T1):

MVA/HIV62B vaccine  $1 \times 10^8$  TCID50 to be administered as 1 mL IM in the LEFT deltoid (unless medically contraindicated) at Months 0 and 4

**AND**

Control for AIDSVAX® B/E (Sodium Chloride for Injection USP, 0.9%) to be administered as 1 mL IM in the RIGHT deltoid (unless medically contraindicated) at Months 0 and 4.

#### Group 2

##### Treatment 2 (T2):

MVA/HIV62B vaccine  $1 \times 10^8$  TCID50 to be administered as 1 mL IM in the LEFT deltoid (unless medically contraindicated) at Months 0 and 4

**AND**

AIDSVAX® B/E (600 mcg/mL) to be administered as 1 mL IM in the RIGHT deltoid (unless medically contraindicated) at Months 0 and 4.

#### Group 3

##### Treatment 3 (T3):

MVA/HIV62B vaccine  $1 \times 10^8$  TCID50 to be administered as 1mL IM in the LEFT deltoid (unless medically contraindicated) at Months 0 and 4

**AND**

Control for AIDSVAX® B/E (Sodium Chloride for Injection USP, 0.9%) to be administered as 1 mL IM in the RIGHT deltoid (unless medically contraindicated) at Months 0 and 4.

**Treatment 4 (T4):**

MVA/HIV62B vaccine  $1 \times 10^8$  TCID50 to be administered as 1mL IM in the LEFT deltoid (unless medically contraindicated) at Months 0 and 4

**AND**

AIDSVAX® B/E (600 mcg/mL) to be administered as 1 mL IM in the RIGHT deltoid (unless medically contraindicated) at Months 0 and 4.

**Group 5**

**Treatment 5 (T5):**

Control for MVA/HIV62B vaccine (Sodium Chloride for Injection USP, 0.9%) to be administered as 1mL IM in the LEFT deltoid (unless medically contraindicated) at Months 0 and 4

**AND**

AIDSVAX® B/E (600 mcg/mL) to be administered as 1 mL IM in the RIGHT deltoid (unless medically contraindicated) at Months 0 and 4.

**8.2 Study product formulation**

**8.2.1 MVA/HIV62B vaccine (labeled as MVA/HIV62B  $10^8$  TCID50/mL. GeoVax™, Inc.)**

MVA/HIV62B is supplied as an opalescent to cloudy, colorless to off-white or light yellow suspension in single-dose vials containing a volume to deliver 1 mL of  $1 \times 10^8$  TCID50/mL. The aqueous suspension may contain small visible particles. The vials containing study product must be stored frozen at -70°C or colder.

**8.2.2 Control for MVA/HIV62B vaccine (Sodium Chloride for Injection USP, 0.9%)**

Sodium Chloride for Injection USP, 0.9% will be used as the Control for MVA/HIV62B and must be stored as directed by the manufacturer.

**8.2.3 AIDSVAX® B/E (labeled as AIDSVAX® B/E active (MN/A244 rgp 120/HIV-1))**

AIDSVAX® B/E is supplied as a sterile suspension in single-use glass vials containing a volume to deliver 1 mL (300mcg/mL) of each rgp120/HIV-1 protein adsorbed onto a total of 600 mcg aluminum hydroxide gel adjuvant. The product must be stored upright and kept refrigerated (2° to 8°C). DO NOT FREEZE. DO NOT SHAKE.

### 8.2.4 Control for AIDSVAX® B/E (Sodium Chloride for Injection USP, 0.9%)

Sodium Chloride for Injection USP, 0.9% will be used as the Control for the AIDSVAX® B/E. Product must be stored as directed by the manufacturer.

## 8.3 Preparation of study products

### 8.3.1 MVA/HIV62B

One vial of MVA/HIV62B (labeled as MVA/HIV62B  $10^8$  TCID50/mL) will be needed to prepare this dose. Prior to injection, the pharmacist will remove the vial from the freezer and allow it to thaw in a 2° to 8° C refrigerator for 2 to 18 hours. During this 2 to 18 hour period, if the vaccine is not completely thawed and a volunteer is ready to be vaccinated, the pharmacist may hold the vial in his/her hand to complete the thawing process. The thawed MVA/HIV62B vaccine can be held at 2° to 8° C for up to 5 days (120 hours) after removal from the freezer. Do not STORE at room temperature.

Immediately prior to withdrawing a 1 mL dose into a 3 or 5 mL syringe, the vial should be removed from the refrigerator and inverted gently several times. DO NOT SHAKE. Using aseptic technique, the pharmacist should withdraw the entire contents of the vial, up to 1 mL, into a 3 or 5 mL syringe. The syringe containing the product must not be held at room temperature. Once drawn into the syringe, the vaccine should be kept cold (2° to 8°C) until it is ready to be injected into the participant. The syringe should be labeled as “MVA/HIV62B vaccine  $1 \times 10^8$  TCID50 or Control” and must also be labeled for administration in LEFT deltoid. The syringe should also be labeled with a 24 hour expiration date from the time product was withdrawn from the thawed vial into the syringe. (Note: If the vaccine is not withdrawn from the vial until 96 hours or more after removal from the freezer, then the actual expiration date/time should be used). The syringe must have an overlay to maintain blinding.

Any unused portion of entered vials or expired prefilled syringes should be disposed of in accordance with institutional or pharmacy policy.

### 8.3.2 Control for MVA/HIV62B (Sodium Chloride for Injection USP, 0.9%)

Sodium Chloride for Injection USP, 0.9% will be needed to prepare this dose. Prior to injection, the Pharmacist will remove the product from storage and place it in a 2° to 8°C refrigerator for 2 to 18 hours.

Immediately prior to withdrawing a 1 mL dose into a 3 or 5 mL syringe, the vial should be removed from the refrigerator. Using aseptic technique, the pharmacist should withdraw 1 mL, into a 3 or 5 mL syringe. The syringe containing the product must not be held at room temperature. Once drawn into the syringe, the control should be kept cold (2° to 8°C) until it is ready to be injected into the participant. The syringe should be labeled as “MVA/HIV62B vaccine  $1 \times 10^8$  TCID50 or Control” and must also be labeled for administration in LEFT deltoid. The syringe should also be labeled with a 24 hour expiration date from the time product was withdrawn from the refrigerated vial into the syringe. (Note: If the placebo is not withdrawn from the vial until 96 hours or more after removal from storage, then the actual expiration date/time should be used). The syringe must have an overlay to maintain blinding.

Any unused portion of entered vials or expired prefilled syringes should be disposed of in accordance with institutional or pharmacy policy.

### 8.3.3 AIDS VAX® B/E

One vial of AIDS VAX® B/E will be needed to prepare the dose. Prior to dispensing, the pharmacist will remove the study product from the refrigerator to allow the vial to equilibrate to room temperature for at least 20 minutes. The pharmacist must then:

- 1) Gently roll the vial horizontally between the palms or on a hard surface for approximately 10 seconds to wet the interior wall of the vial and to suspend the material.
- 2) Grasp the vial by the sides. Firmly and forcefully tap the bottom of the vial on a solid surface such that the vial hits squarely on a solid surface, in a rapid series of three (3) taps. Tap with enough force to dislodge any material that may be on the sides of the vial while using care not to chip or break the vial.
- 3) Repeat the gentle rolling and forceful tapping two more times, resulting in one (1) cycle of 9 taps.
- 4) Visually inspect the neck of the vial for presence or absence of product-related material (grayish film) as well as the sides of the vial. Vaccine that is stored at 2°C to 8°C can form an appearance of a cloudy ring or ‘halo’ on the vial neck and/or have product related material adhering on the sidewalls. If either condition is observed, the pharmacist should continue to follow the steps as directed below to dislodge and uniformly resuspend such product-related material.
- 5) If the product-related material still persists at the neck/sides of the vial at the end of the first cycle, repeat steps 1 to 4, for up to two (2) more cycles.
- 6) If the product-related material is still visible at the end of the third repeated cycle DO NOT use the vial.

After completing these steps, the pharmacist, using aseptic technique, will gently roll the mixture in the vial one more time and then withdraw 1 mL into a 3 or 5 mL syringe using a 21 or 23 gauge needle. The syringe should be labeled as “AIDS VAX B/E 600 mcg or Control 1 mL”. The syringe must also be labeled for administration in RIGHT deltoid. The syringe must have an overlay to maintain blinding.

The study product should be administered as soon as possible after being drawn into the syringe.

Any unused portion of entered vials or expired prefilled syringes should be disposed of in accordance with institutional or pharmacy policy.

### 8.3.4 Control for AIDS VAX® B/E (Sodium Chloride for Injection USP, 0.9%)

Sodium Chloride for Injection USP, 0.9% will be needed to prepare the dose. The pharmacist using aseptic technique, will withdraw 1 mL of Sodium Chloride for Injection USP, 0.9% into a 3 or 5 mL syringe using a 21 or 23 gauge needle. An overlay must be applied to the syringe.

The syringe should be labeled as “AIDSVAX B/E 600 mcg or Control 1 mL”. The syringe must also be labeled for administration in RIGHT deltoid. The syringe must have an overlay to maintain blinding.

The study product should be administered as soon as possible after being drawn into the syringe.

Any unused portion of entered vials or expired prefilled syringes should be disposed of in accordance with institutional or pharmacy policy.

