### 9.3 Enrollment and vaccination visits

Enrollment is simultaneous with first vaccination. The time interval between randomization and enrollment should not exceed 4 working days. The HVTN CRS registers the participant by scheduling the day 0 visit (enrollment) via the Web-based randomization system, and requests the randomization assignment. Circumstances may require a participant's enrollment visit to be changed. This may exceed the 4-day randomization time limit.

At all vaccination visits, the following procedures are performed before vaccination:

- Abbreviated physical examination, including weight, vital signs, and a symptom-directed evaluation by history and/or appropriate physical exam based on participant self-reported symptoms or complaints;
- Assessment of baseline reactogenicity parameters;
- Assessment of concomitant medications (as described in Section 9.2);
- Cardiac symptom assessment;
- Assessment of any new or unresolved AEs/intercurrent illnesses; and
- Urine or serum pregnancy test (for participants who were born female). Persons who are NOT of reproductive potential due to having undergone total hysterectomy or bilateral oophorectomy (verified by medical records), are not required to undergo pregnancy testing.
- Optional mucosal specimen collection
- Clinical laboratory tests for study participants who agree to provide (semen, rectal, or cervicovaginal) mucosal secretion samples, including:
  - Syphilis
  - Gonorrhea and chlamydia
  - Trichomonas vaginalis (for participants providing cervicovaginal samples),
  - Bacterial vaginosis (for participants providing cervicovaginal samples),
  - Yeast (for participants providing cervicovaginal samples, if clinically indicated).

Following completion of all procedures in the preceding list, and if results indicate that vaccination may proceed, vaccination is prepared and administered (Sections 8.3 and 8.4).

Administration of all injections during a vaccination visit must be accomplished within 1 calendar day.

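### Preparation timing is not matched between AIDSVAX B/E and its saline control, so the wait for the right-arm syringe can hint at assignment before subjective reactogenicity is scored

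*Combined protocol and SAP*

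**What the plan says.** **AIDSVAX B/E (Section 8.3.3).** Before dispensing, "the pharmacist will remove the study product from the refrigerator to allow the vial to equilibrate to room temperature for at least 20 minutes". Rolling and tapping follow: "Repeat the gentle rolling and forceful tapping two more times, resulting in one (1) cycle of 9 taps". If material is still visible, the pharmacist is to "repeat steps 1 to 4, for up to two (2) more cycles", and the vial may not be used if material remains after the third cycle.

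**Control for AIDSVAX B/E (Section 8.3.4).** "The pharmacist using aseptic technique, will withdraw 1 mL of Sodium Chloride for Injection USP, 0.9% into a 3 or 5 mL syringe". The syringe is labelled and given an overlay. No hold or equilibration is specified.

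**Both right-arm syringes.** "The study product should be administered as soon as possible after being drawn into the syringe". This instruction appears in both 8.3.3 and 8.3.4, and neither gives a period for which a filled syringe may be kept.

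**The MVA pair (Sections 8.3.1 and 8.3.2).** Here the control does copy the active product: "the Pharmacist will remove the product from storage and place it in a 2° to 8°C refrigerator for 2 to 18 hours". It is also kept cold and carries the same label and the same 24-hour expiry. Thawed MVA may be held for up to 5 days.

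**Order of events (Section 9.3).** Once the pre-vaccination procedures are complete and allow it, "vaccination is prepared and administered (Sections 8.3 and 8.4").

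**Blinding (Sections 6.3, 8.3 and 8.4).** Participants and site staff other than pharmacists are blinded. The stated safeguards are overlays, shared labels, the same needle gauge and syringe rolling for both right-arm products, and a ban on pharmacy staff discussing assignments with other site staff. None concerns time.

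**The concern.** The protocol matches control to active handling in full for one product pair and only in part for the other. The unmatched element, elapsed time, is one that participants and clinic staff can observe. It also follows the contrast the trial is built on: whether AIDSVAX B/E is part of the boost.

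The exposed outcome is reactogenicity, which is part of primary endpoint 1 (Section 5.1). Clinic staff score it 25 to 60 minutes after injection, and it is then followed through day 3, largely from the participant's symptom log (Sections 9.3 and 9.10). All of this comes after any wait. Pain, tenderness, malaise, myalgia and headache are matters of judgement, and Section 6.4.3.1 plans Kruskal-Wallis tests of severity between groups. If expectation moved some of those scores, a difference between regimens could be partly an artefact of knowing the assignment.

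**Working it through.** The plan states no figure on this point, so there is none to reproduce. The check sets the handling steps side by side, adds up the stated times, and asks which groups a wait could distinguish.

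**1. Handling steps**

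| Step | AIDSVAX B/E (8.3.3) | Its control (8.3.4) | MVA (8.3.1) | Its control (8.3.2) |
|---|---|---|---|---|
| Hold before drawing up | at least 20 min, room temperature | none stated | 2–18 h refrigerator thaw | 2–18 h refrigerator |
| Resuspension | 1–3 roll-and-tap cycles, final roll | none | gentle inversion | none |
| After drawing up | give as soon as possible | give as soon as possible | kept cold, 24 h label | kept cold, 24 h label |
| Overlay and shared label | yes | yes | yes | yes |

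The left-arm syringe can be ready ahead of the visit in every group. The right-arm syringe cannot be filled far ahead, so any delay that depends on assignment falls there.

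**2. Time for the AIDSVAX steps**

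Stated inputs: a 20-minute hold, and three rolls of about 10 s and three tap series per cycle. Assumed, because the protocol gives no durations: 2–5 s per tap series, 0–30 s per inspection, and 10 s for the final roll.

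Seconds = 20 × 60 + cycles × [3 × (10 + tap) + inspection] + 10

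- Shortest (one cycle, 2 s, 0 s): 1200 + 36 + 10 = 1246 s = 20.8 min
- Longest (three cycles, 5 s, 30 s): 1200 + 225 + 10 = 1435 s = 23.9 min

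If equilibration is already complete when the syringe is requested, only rolling, tapping and inspection remain: 46 to 235 s, or about 1 to 4 minutes.

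**3. What a wait could reveal**

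From Table 3-1, Groups 1 and 3 receive the AIDSVAX control (20 + 20 = 40) and Groups 2, 4 and 5 receive AIDSVAX (60). Prior regimen is an entry criterion and the randomization stratum. If the wait were fully informative:

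- among prior MMM recipients it would tell Group 1 from Group 2;
- among prior DDMM recipients it would identify Group 3, but would leave Groups 4 and 5 (40 people) indistinguishable.

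That makes 60 of 100 identified and 40 narrowed to two options. It is an upper limit, not an expectation.

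**4. What bias would do to the test: an illustration only**

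Assume the same true severity in both arms (45/35/17/3% none/mild/moderate/severe). A fraction of participants infer their arm, and 20% or 40% of those report one grade in the expected direction (up if AIDSVAX, down if control). The table shows how often Kruskal-Wallis gives p ≤ 0.05 in simulated trials.

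| Fraction who infer their arm | 20 v 20 | 40 v 40 |
|---|---|---|
| none | about 5% | about 5% |
| 10% | about 5% | about 5–6.5% |
| 50% | about 8–19% | about 12–34% |

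The result depends almost entirely on the fraction who infer their arm and the shift. The documents supply neither.

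**The case against.** The strongest reply is that the documents do not establish a longer wait. Section 8.3.3 ties the 20 minutes to the time before dispensing and sets no trigger and no upper limit. The instruction to inject promptly runs from filling the syringe, not from taking out the vial. The pharmacist knows the assignment, enrollment follows randomization, and the second vaccination is a scheduled visit. The vial can therefore equilibrate while the visit procedures are under way, leaving a difference of a few minutes.

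Section 9.3 also refers to all of Section 8.3. Read literally, the 2-hour MVA step would begin after the procedures too, and would hide the 20 minutes in every group.

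Further, visit length varies with examinations, pregnancy tests and optional mucosal sampling. A participant receives the same regimen at both visits and so has no contrast of their own. Temperature and lesion size are measured, AEs are not formally tested between groups, and primary endpoint 2 is laboratory-based. The Pharmacy Guidelines or the Study Specific Procedures, which are not among the documents, may already deal with timing.

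Most of this stands. A reader might infer that AIDSVAX recipients necessarily wait at least 20 minutes longer, that the wait separates the arms completely, or that the false-positive rate rises to some particular figure. The text supports none of these. Nor is it right to say that the control needs no preparation: it must be drawn up, labelled and covered.

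What survives is narrower. Starting early is permitted but not required, so whether the cue exists is left to each site's habit. MVA may expressly be readied days ahead, so the literal reading of Section 9.3 is not one that sites need follow. Nothing in the protocol equalises the timing.

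**Conclusion.** The mismatch between 8.3.3 and 8.3.4 is plain in the text, and the protocol's own treatment of the MVA control shows the standard it falls short of. At a site that begins preparation on request, the wait can be a cue to AIDSVAX or no AIDSVAX for participants and blinded clinic staff, at either vaccination, before subjective symptoms are scored.

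The size of the cue is about 21 to 24 minutes against no stated minimum, given the assumed tapping and inspection times. It shrinks to about 1 to 4 minutes where equilibration starts early. It bears on 40 control and 60 AIDSVAX recipients and does not separate Group 4 from Group 5. Any resulting bias in reactogenicity cannot be sized from the documents: the illustration runs from near-nominal error rates to several times nominal, according to what is assumed.

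This is a possible weakness in the blind that is cheap to close. It is not evidence that the blind fails.

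**What to change.** Add to Sections 8.3.3 and 8.3.4 that the right-arm syringe, active or control, is released on the same schedule for every participant. Either of two arrangements would do:

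- the control is held, before drawing up, for the same minimum 20 minutes plus an allowance for preparation; or
- in all groups, equilibration or the matched control hold starts before the visit procedures end, with release at one common interval after the request.

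Placing the hold before drawing up leaves the instruction on prompt injection intact. Add also that vial rolling and tapping are done out of sight and hearing of participants and clinic staff. If the Study Specific Procedures already cover timing, a cross-reference in Section 8.3 is enough.

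The cost is pharmacy wording and some added waiting: mainly at up to 80 control visits (40 participants × 2), by about 20 minutes under the first arrangement. A fixed interval that allows for repeat cycles may also add a few minutes at the 120 AIDSVAX visits (60 × 2). Doses and handling of the active products do not change.
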